Participants will complete a within-subjects online randomized experiment. After providing informed consent, participants will view and rate messages on perceived message effectiveness (primary outcome) and perceived awareness of the harms of social media (secondary outcome). Participants will view messages about 9 topics: 8 warning topics and 1 control topic. The 8 warning topics include 7 potential mandatory social media warnings (including the topics of depression and anxiety, body image, addiction, sleep, mental health harms to children, not been proven safe, and California's proposed warning) and 1 voluntary warning (similar to a message used on TikTok to encourage users to take breaks). For each topic, participants will view 1-2 messages and respond to survey items about that message. All messages will be shown in random order.

Statistical Considerations

General Principles

We will use a two-sided critical alpha of 0.05 as a criterion for all tests of statistical significance. All confidence intervals presented will be 95% and two-sided. We will follow intention-to-treat principles, including all participants who fully enroll in the study. We expect minimal missing data based on prior similar studies¹⁻³ but missing data will be accounted for under maximum likelihood assumptions in our mixed effects regression analysis of primary and secondary outcomes.

Primary Outcome

The primary outcome is perceived message effectiveness for discouraging social media use. We will measure perceived message effectiveness with 1 item adapted from prior studies,^{4,5} “How much does this message discourage you from wanting to use social media?” Response options will range from not at all (1) to a great deal (5).

Secondary Outcomes

The secondary outcome is reported increased awareness of the harms of social media. We will measure perceived awareness of the harms of social media with 1 item, “How much does this message increase your awareness of the harms of using social media?” Response options will range from not at all (1) to a great deal (5).

Statistical Methods

We plan to present results in two papers.

Paper 1 Analyses

1. Analyses of the primary outcome

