 - a. We will use mixed effects linear regression to **evaluate the effect of each warning topic compared to the control topic on the primary outcome of perceived message effectiveness**. We will regress perceived message effectiveness on a set of indicator variables representing each social media warning topic (e.g., depression and anxiety, negative body image, sleep, etc.), excluding the control topic as the referent. We will treat the intercept as random to account for repeated measures within participants. The coefficients on the warning topics will give the average difference in mean perceived message effectiveness between each warning topic and the control topic. Given the exploratory nature of the study, we do not plan to correct *p*-values for multiple comparisons.
 - b. We will use the same mixed effects linear regression model to **evaluate the effect of each potential mandatory warning topic compared to the voluntary warning**.

- c. In exploratory analysis, we will test whether the effects of the warning topics on the primary outcome are possibly moderated by age (treated continuously), gender (male vs. female), and amount of social media use (treated continuously). To test for moderation, we will use mixed effects linear regression, regressing perceived message effectiveness on indicator variables representing each social media warning topic (excluding the control as the referent), the possible moderator, and the interactions between the possible moderator and the warning topics. We will center variables prior to analysis. We will use separate models for each moderator. We will test the joint significance of the interaction terms.
- d. We will also **descriptively rank the warning topics** on the primary outcome of perceived message effectiveness. We will estimate mean perceived message effectiveness for each social media warning topic (averaging across messages for each topic) and rank those means.

2. Analyses of the secondary outcome:

- a. We will use mixed effects linear regression to **evaluate the effect of each social media warning topic compared to the control topic on the secondary outcome of awareness of the harms or social media**. We will use the same approach as described for the primary outcome (see no. 1 above).
- b. We will use the same mixed effects linear regression model to **evaluate the effect of each potential mandatory warning topic compared to the voluntary warning**.

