- c. We will **descriptively rank the social media warning topics** on the secondary outcome of perceived awareness of the harms of social media. We will estimate mean perceived awareness of the harms of social media for each topic (averaging across messages for each topic) and rank those means.

Paper 2 Analyses

1. Analyses of the primary outcome:

- a. We will test whether the effects of the social media warning topics in this study with human participants differ from the effects observed in a separate experiment conducted with artificial intelligence (AI) personas. We will compare the coefficient on each warning topic estimated in this study to the corresponding coefficient estimated in the separate experiment conducted with AI personas. We will pool data from this study with the data from the separate experiment conducted with AI personas and run a mixed effects linear regression, regressing perceived message effectiveness on indicator variables for each warning topic (excluding the control as the referent), an indicator variable for sample (i.e., whether the observation is from this study vs. the AI study), and the interaction between warning topic and sample. All variables will be centered. We will examine the coefficients on the interaction terms.

- b. We will compare how our human participants rate social media warnings we refined using AI personas to those we selected *a priori* and did not refine using AI. We will make this comparison both overall (pooling across all warning topics) and within each warning topic. These analyses will only include ratings from the 6 warning topics for which we tested both AI-developed and human-developed messages (depression and anxiety, negative body image, addiction, sleep, mental health harms to children, and not been proven safe).
 - i. First, we will use mixed effects regression, regressing perceived message effectiveness on an indicator variable for message source (AI-developed vs. human-developed) and treating the intercept as random. The coefficient on the indicator variable will indicate the average difference in means between AI-developed vs. human-developed messages.

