 - ii. Second, we will run a set of mixed effects regressions, one for each warning topic. Each regression will regress perceived message effectiveness on an indicator variable for message source (AI-developed vs. human-developed), treating the intercept as random. The coefficient on the indicator variable will indicate the average difference in means between AI-developed vs. human-developed messages.

Sample Size Needs

We plan to collect data from 1,000 participants. We used G*Power⁶ to estimate sample size needs to detect an effect of each social media warning topic vs. control using ANOVA repeated measures (testing of within-subject factors). Assuming alpha=0.05, 2 measurements (given each contrast will compare 2 topics to one another), and a conservative correlation among repeated measures of 0.5 (based on prior studies⁷⁻⁹), a sample size of 900 would yield 85% power to detect effects of $f=0.05$ ($d=0.10$) or larger. This effect size would be considered small¹⁰ and is conservative based on our prior message development studies.^{8,9,11} We will recruit 1,000 participants to account for potential missing data.

Exclusions and Outliers

We will exclude human participants who do not complete the survey or who complete the survey implausibly quickly (defined as <1/3 of the median completion time). We will winsorize outlier values defined as more than 3 interquartile ranges below or above the 25th and 75th percentiles of the observed distributions (i.e., Tukey far outliers). These participants and winsorized observations will be included in the analysis.

References

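### Does the 3-IQR winsorizing rule, which names no variables, put the 1–5 outcome ratings at risk?

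*SAP*

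**What the plan says.** The only outlier text is in Exclusions and Outliers: "We will winsorize outlier values defined as more than 3 interquartile ranges below or above the 25th and 75th percentiles of the observed distributions". The next sentence keeps the altered values: "These participants and winsorized observations will be included in the analysis". Neither sentence lists the variables concerned or the level at which a distribution is formed.

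The primary outcome (Primary Outcome section) is one item, "How much does this message discourage you from wanting to use social media", with five response options from 1 to 5. The secondary outcome is also one item on a 1–5 scale. On presentation, the Study Protocol section says "For each topic, participants will view 1-2 messages and respond to survey items about that message". Paper 1, analysis 1a, regresses the rating on topic indicators, "excluding the control topic as the referent", with a random intercept per participant. Analysis 1c treats two further variables as continuous: age, which eligibility limits to 13–29, and amount of social media use.

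**The concern.** A far-outlier rule suits an open-ended quantity such as hours of use. On a five-option item every answer is valid, so there is nothing for the rule to correct. Because the rule names no variables, a literal reader could apply it to the outcomes. Because it names no level, that reader could also take quartiles separately for each topic.

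The control topic is where this could hurt. It is the referent for every control contrast on both outcomes and for the human-versus-AI-persona comparison in Paper 2, 1a. If most participants answered 1 to the control message on an item, per-topic quartiles would both be 1 and every higher control answer would be reset to 1. Each contrast with an unclipped warning topic would then be too large. If a warning topic were clipped as well, a real difference could vanish.

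**Working it through.** **The plan's own figure.** Inputs from Sample Size Needs: N = 900, f = 0.05 (d = 0.10), 2 measurements, correlation 0.5, alpha 0.05. Noncentrality = f² × N × m / (1 − ρ) = 0.0025 × 900 × 2 / 0.5 = 9. With F(1, 899) the power is 0.850, so the stated 85% reproduces. It does not depend on the outlier rule.

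**The fences on a 1–5 item.** Let L and U be the lower and upper quartiles. The fences are L − 3(U − L) and U + 3(U − L). There are 15 whole-number pairs with L ≤ U.

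- In the 10 pairs with IQR ≥ 1, no rating from 1 to 5 lies beyond a fence. The tightest are (1, 2), with upper fence 2 + 3 = 5, and (4, 5), with lower fence 4 − 3 = 1. The rule requires more than 3 IQRs, so 5 and 1 are not touched.
- In the 5 pairs with IQR = 0, both fences equal the quartile and the other four answers are all reset to it.

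Interpolated quartiles between whole numbers need an exact tie (for example, exactly 750 ones among 1,000 ratings) and are set aside.

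**Per-topic quartiles (assumed distributions, 1,000 control ratings).** Let p be the share answering 1. For p below 75% (checked at 50%, 60%, 70% and 74%) nothing changes. Above 75% the control mean becomes 1.00, and the upward bias in a contrast with an unclipped topic is (1 − p) × mean excess over 1 among the other answers. Three assumed shapes for answers 2 to 5:

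- 10/7/4/3: excess (10 + 14 + 12 + 12)/24 = 2.0
- 14/6/3/1: excess (14 + 12 + 9 + 4)/24 = 1.625
- flat: excess (1 + 2 + 3 + 4)/4 = 2.5

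| p | 10/7/4/3 | 14/6/3/1 | flat |
|---|---|---|---|
| 74% | 0 | 0 | 0 |
| 76% | 0.24 × 2.0 = 0.48 | 0.24 × 1.625 = 0.39 | 0.24 × 2.5 = 0.60 |
| 90% | 0.10 × 2.0 = 0.20 | 0.16 | 0.25 |
| 95% | 0.05 × 2.0 = 0.10 | 0.08 | 0.13 |

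With the 10/7/4/3 shape and a warning topic also near the floor:

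- Control 80% and warning 74% at 1: means 1.40 and 1.52. The difference of 0.12 becomes 1.52 − 1.00 = 0.52.
- Control 90% and warning 80% at 1: means 1.20 and 1.40. The difference of 0.20 becomes 0.

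**Quartiles pooled over all ratings of the item.** Paper 2, 1b, gives six topics with both an AI-developed and a human-developed message: 6 × 2 = 12 messages. The California, voluntary and control topics add 1 or 2 each, so 15 to 18 messages in all, assuming each participant rates every one. The control share c of ratings runs from 1/17 to 2/16. Even if every control rating were 1, an upper quartile of 1 needs a share of warning ratings at 1 of (0.75 − c)/(1 − c):

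- c = 1/17: 0.6912/0.9412 = 0.734
- c = 2/16: 0.625/0.875 = 0.714

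With control floors of 76% or 90% and warning floors of 30%, 50% or 70%, no rating changed. Away from the floor, a pooled IQR of 0 would need at least half of all ratings on one value, with no more than a quarter on either side.

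**The case for a change.** The strongest case for acting is that the SAP presents itself as the analysis fixed in advance, yet two analysts following it faithfully could treat the primary outcome differently and choose after seeing the data. The rule has no legitimate work to do on a five-option item, so exempting the ratings would cost one sentence and lose nothing. In the bad case the distortion is several times the planned detectable effect.

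The arithmetic stands, and so does the observation that scope and level are unstated. The likelihood of harm does not. Three things must coincide: the rule is applied to the five-option outcomes, quartiles are formed per topic or message, and more than about 75% of control ratings are 1. The SAP states none of them. The largest biases occur just past the 75% threshold, and the two examples with both topics near the floor also need 74% to 80% of ratings of a warning topic to be 1. Clipping the control leaves the point estimates of the mandatory-versus-voluntary contrasts, the ranking of warning topics and the AI-versus-human message comparison unchanged. Where warnings are rated well above control, only the size of the effect would be overstated. The bad case would also be plain to see, since the control ratings would have a standard deviation of exactly 0.

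Confining the rule to social media use alone would presume an intent that the SAP does not state. Age is also treated as continuous, and the document does not say how social media use is measured.

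**Conclusion.** No change follows. Each outcome enters its model as a single variable with topic as a predictor, so the ordinary meaning of an observed distribution is one per variable. On that reading the rule almost certainly leaves every rating as given, and its only practical effect is on a measure with a long tail, where such a rule makes sense. An analyst who leaves the five-option items alone reaches the same data.

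The likely size is therefore zero. A shift of about 0.1 to 0.6 points arises only with per-topic or per-message quartiles and a control floor above about 75%, and the documents give no rating distribution to support that. For scale, d = 0.10 is about 0.10 to 0.13 points at an assumed SD of 1.0 to 1.3. The conclusion rests on the one-distribution-per-variable reading and on warning ratings not being piled up at 1. The point is a missing detail, not a contradiction or a wrong figure, and the stated power is unaffected.
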